13.1 Effectiveness

Outcomes at 12 months are binary and are denoted "E" (for having experienced a primary outcome Event, e.g., AF recurrence) or "N" (for not having experienced an event). At any sample size look, many subjects will not have completed 12 months, and the 12-month outcomes for those subjects will be imputed according to statistical modeling, as described below.

At the time of analysis, and separately for each treatment group, subjects will fall into one of the following categories:

- A. Final status (E or N) is known. This can happen because the subject has had a known primary event at any time up through the 12-month assessment. It can also happen if the subject is event-free as of the 12-month assessment.
- B. Subject is censored without known event prior to the 12-month assessment. Such subjects will have their 12-month outcome imputed to be E with a probability that is subject-specific and is based on how long that subject has been followed and also on the event-free survival experience of other subjects (in the same treatment group), calculated via a Bayesian piecewise exponential survival model, as described below. Imputed outcomes are based on the subject-specific survival probabilities at Follow-up Day 360.

In this survival model, Time 0 days corresponds to the procedure date. The hazard function $h(\tau)$ is piecewise constant over the intervals $(0, 90 \text{ days}]$, $(90, 104 \text{ days}]$, $(104, 150 \text{ days}]$, $(150-210 \text{ days}]$, and $(210-360 \text{ days}]$. Justification for this partition of the time axis is given later in this section. Specifically, let the survival function $S(t)$ represent the probability that a subject in this category is event-free at time t , where

$$S(t) = e^{-\int_0^t h(\tau)d\tau}, \text{ and}$$

$$h(\tau) = \begin{cases} \lambda_1, & \tau \in (0, 90 \text{ days}] \\ \lambda_2, & \tau \in (90, 104 \text{ days}] \\ \lambda_3, & \tau \in (104, 150 \text{ days}] \\ \lambda_4, & \tau \in (150, 210 \text{ days}] \\ \lambda_5, & \tau \in (210, 360 \text{ days}] \end{cases}$$

Let $\Lambda = \{\lambda_1, \lambda_2, \lambda_3, \lambda_4, \lambda_5\}$. We assign each λ_i ($i = 1, 2, 3, 4, 5$) an independent Gamma prior distribution, and because of the well-known Poisson-Gamma conjugacy, the posterior distribution $f(\lambda_i | \text{data})$ also follows a Gamma distribution. Samples from the posterior distributions of $\lambda_1, \lambda_2, \lambda_3, \lambda_4$, and λ_5 can be drawn directly, without the need for Markov chain Monte Carlo techniques.

For a subject j censored at $R_j < 360$ days, the probability θ_j that this subject has an event by Day 360 can be computed as

$$\begin{aligned}\theta_j &= \text{Prob}[T \leq 360 \mid T > R_j] \\ &= \text{Prob}[R_j < T \leq 360] / \text{Prob}[T > R_j] \\ &= (S(R_j) - S(360)) / S(R_j)\end{aligned}$$

where $S(t) = \exp(-H(t))$ and $H(t)$ is the cumulative hazard function

$$\begin{aligned}H(t) &= \int_0^t h(\tau) d\tau \\ &= \begin{cases} \lambda_1 t, & t \in [0, 90] \text{ days} \\ 90\lambda_1 + (t - 90)\lambda_2, & t \in (90, 104] \text{ days} \\ 90\lambda_1 + (104 - 90)\lambda_2 + (t - 104)\lambda_3, & t \in (104, 150] \text{ days} \\ 90\lambda_1 + (104 - 90)\lambda_2 + (150 - 104)\lambda_3 + (t - 150)\lambda_4, & t \in (150, 210] \text{ days} \\ 90\lambda_1 + (104 - 90)\lambda_2 + (150 - 104)\lambda_3 + (210 - 150)\lambda_4 + (t - 210)\lambda_5, & t \in (210, 360] \text{ days} \end{cases}\end{aligned}$$

The distribution of θ_j can thus be computed from the piecewise constant form of $h(\tau)$ to be a function of Λ and R_j . This can be easily accomplished multiple times by first drawing gamma deviates for $\lambda_1, \lambda_2, \lambda_3, \lambda_4$, and λ_5 and subsequently transforming these into samples from the subject-specific distribution of θ_j for subject j . The unobserved final binary event status (E, N) for subject j is then imputed multiple times from a Bernoulli distribution with parameter θ_j (once for each sampled value of θ_j).

Prior Distributions in the Predictive Model

Parameters $\lambda_1, \lambda_2, \lambda_3$, and λ_4 are independently assigned a $\text{Gamma}(0.5, 0.001)$ prior distribution. This approximates the Jeffreys non-informative prior but is proper. Because of Poisson-Gamma conjugacy, the posterior distribution $f(\lambda_i \mid \text{data})$ follows a $\text{Gamma}(0.5 + D_i, 0.001 + T_i)$ distribution, where D_i is the number of events that occurs in interval i and T_i is the total amount of follow-up over all subjects in interval i (in days).

Parameter λ_5 needs special consideration. At the time of the interim sample size looks, it is expected that there will not be enough follow-up experience in the 210-to-360-day window to reliably estimate the λ_5 parameter without some moderate help from an informative prior. Therefore, λ_5 is assigned a $\text{Gamma}(5, 10000)$ prior distribution, equivalent to observing 5 events in 10000 patient-days, or 5 events in about 67 subjects followed for the entirety of the 210-to-360-day interval. The influence of this prior can be understood by recognizing that the ratio $S(360)/S(210) = \exp(-\lambda_5 \times (360 - 210))$, where $\lambda_5 \sim \text{Gamma}(5, 10000)$, as shown in

Figure 1. In other words, $S(360 \text{ days})$ is expected to have decreased to roughly 90–95% of the value at $S(210 \text{ days})$.

This is consistent with the results of Fire and Ice³ in **Figure 2**, where it is observed that $1 - S(360) \approx 0.35$ and $1 - S(210) \approx 0.29$, leading to $S(360)/S(210) = 0.65/0.71 = 0.916$. Other trials^{14,16,17,18} have shown similar trends in the 210-to-360-day window.

Figure 1 Prior distribution for survival decrease between 210 and 360 days: $S(360)/S(210) = \text{Exp}(-\lambda_5 \times (360 - 210))$, where $\lambda_5 \sim \text{Gamma}(5, 10000)$

[figure not shown]
[figure not shown]

Figure 2 Time to Primary Outcome from Fire and Ice³

Rationale for the Time Axis Partition of the Piecewise Exponential Model

The piecewise exponential model has a hazard function that is piecewise constant (or “flat”). With a fine enough partition, a piecewise exponential model can be used to approximate any hazard function⁹. However, to produce stable estimates of hazard parameters, a reasonable number of events must be observed in each “piece” of the partition, so too fine a partition is impractical. The partition (0–90, 90–104, 104–150, 150–210, 210–360 days) is justified primarily by evidence observed in the Fire and Ice trial³, where the time to primary event is depicted in **Figure 2** (from reference 3), in which it is observed that the shapes of the curves appear to change at approximately 90 days (the end of the blanking period), two weeks later (104 days), and around the 6-month visit window (starting at 180 – 30 = 150 days and ending at 180 + 30 = 210 days). From 210 to 360 days, the curve rises at a reasonably constant exponential rate. A similar assessment of the time-to-event curves from other trials^{14,16,17,18} indicates that, although this partition of the time axis may be finer than necessary, it can also appropriately model their respective hazards.

Censoring Procedures

The model in part B, above, is based on censoring or event times up through post-blanking day Day 360. Subjects without a known event will be considered censored at the later of their last Event Monitor or last Holter Monitor. Since the 12-month follow-up window extends to Follow-up Day 390, all events and censoring times > 360 days will be assigned a time of 360 Days when fitting the piecewise exponential models.

Predictive Probabilities and Posterior Inference

At every analysis, the imputations described above are executed $M=5000$ times, resulting in M completed datasets, filled with only E or N final outcome values. With the $\text{Beta}(0.5, 0.5)$ prior distributions specified in Section 9.1, each of the M completed datasets implies a conjugate Beta posterior distribution for both P_T and P_C . From these, the posterior probability $\text{Pr}(P_T > P_C - 0.15 | m^{\text{th}}$ completed dataset) is computed. This is used in the following ways:

- At each sample size look: The proportion of these M completed datasets that result in $\text{Pr}(P_T > P_C - 0.15 | m^{\text{th}}$ completed dataset) $> \Psi_{\text{eff}}$ is the predictive probability of future success for the effectiveness objective. As described in Section 12, this is used to determine whether to curtail enrollment.
- At the final analysis: For the final analysis, a nearly identical model serves as the “imputer’s model” in a Bayesian multiple imputation that is used to account for any missing data in the inferential tests of the primary endpoint. The critical difference in the two models is that, when used for multiple imputation, all parameters of the piecewise exponential model (including λ_5) are assigned non-informative $\text{Gamma}(0.5, 0.001)$ prior distributions. Averaging the values $\text{Pr}(P_T > P_C - 0.15 | m^{\text{th}}$ completed dataset) over the set of M completed datasets integrates over the posterior predictive distribution of imputed values and results in a final (combined) posterior probability $\text{Pr}(P_T > P_C - 0.15 | \text{data})$ that is then compared to the threshold Ψ_{eff} to determine whether non-inferiority has been statistically established. This is Bayesian multiple imputation.

A test for superiority (secondary objective, conducted at the final analysis) is similar but requires computing $\text{Pr}(P_T > P_C + 0 | m^{\text{th}}$ completed dataset). Averaging these over the set of M completed datasets integrates over the posterior predictive distribution of imputed values and results in a final (combined) posterior probability $\text{Pr}(P_T > P_C | \text{data})$ that is compared to the threshold $\Psi_{\text{eff, sup}}$ to determine whether superiority has been statistically established. This is Bayesian multiple imputation.

13.2 Safety

Statistical modeling for safety is similar to that used for effectiveness, but the piecewise exponential model is simpler. Outcomes at 12 months are binary and are denoted "E" (for having experienced a primary outcome Event) or "N" (for not having experienced an event). At any sample size look, many subjects will not have completed 12 months, and the 12-month outcomes for those subjects will be imputed according to statistical modeling, as described below.

At the time of analysis, and separately for each treatment group, subjects will fall into one of the following categories:

- A. Final status (E or N) is known. This can happen because the subject has had a known primary event at any time up through the 12-month assessment. This can also happen if the subject is event-free as of the 12-month assessment.
- B. Subject is censored without known event prior to the 12-month assessment. Such subjects will have their 12-month outcome imputed to be E with a probability that is subject-specific and is based on how long that subject has been followed and also on the event-free survival experience of other subjects (in the same treatment group), calculated via a Bayesian piecewise exponential survival model, as described below. Imputed outcomes are based on the subject-specific survival probabilities at Follow-up Day 360.

In this survival model, Time 0 days corresponds to the procedure date. The hazard function $h(\tau)$ is piecewise constant over the intervals $(0, 7 \text{ days}]$ and $(7, 360 \text{ days}]$. Specifically, let the survival function $S(t)$ represent the probability that a subject in this category is event-free at time t , where

$$S(t) = e^{-\int_0^t h(\tau) d\tau}, \text{ and}$$

$$h(\tau) = \begin{cases} \lambda_1, & \tau \in [0, 7 \text{ days}] \\ \lambda_2, & \tau \in (7, 360 \text{ days}] \end{cases}$$

Let $\Lambda = \{\lambda_1, \lambda_2\}$. We assign λ_1 and λ_2 a Gamma prior distribution, and because of the well-known Poisson-Gamma conjugacy, the posterior distribution $f(\lambda_i | \text{data})$ also follows a Gamma distribution. Samples from the posterior distributions of λ_1 , and λ_2 can be drawn directly, without the need for Markov chain Monte Carlo techniques.

For a subject j censored at $R_j < 360$ days, the probability θ_j that this subject has an event by Day 360 can be computed as

$$\begin{aligned} \theta_j &= \text{Prob}[T \leq 360 | T > R_j] \\ &= \text{Prob}[R_j < T \leq 360] / \text{Prob}[T > R_j] \\ &= (S(R_j) - S(360)) / S(R_j) \end{aligned}$$

where $S(t) = \exp(-H(t))$ and $H(t)$ is the cumulative hazard function

$$H(t) = \int_0^t h(\tau) d\tau = \begin{cases} \lambda_1 t, & t \in [0, 7] \text{ days} \\ 7\lambda_1 + (t - 7)\lambda_2, & t \in (7, 360] \text{ days} \end{cases}$$

The distribution of θ_j can thus be easily computed to be a function of Λ and R_j . This can be easily and quickly accomplished multiple times by first drawing samples from the gamma posterior distribution of λ_1 and λ_2 and subsequently transforming these into samples from the subject-specific distribution of θ_j for subject j . The unobserved final binary event status (E, N) for subject j is then imputed multiple times from a Bernoulli distribution with parameter θ_j (once for each sampled value of θ_j).

Prior Distributions in the Predictive Model

Parameters λ_1 and λ_2 are independently assigned a $\text{Gamma}(0.5, 0.001)$ prior distribution. This approximates the Jeffreys non-informative prior but is proper. Because of the well-known

Poisson-Gamma conjugacy, the posterior distribution $f(\lambda_i | \text{data})$ follows a $\text{Gamma}(0.5 + D_i, 0.001 + T_i)$ distribution, where D_i is the number of events that occurs in interval i and T_i is the total amount of follow-up over all subjects in interval i (in days).

Rationale for the Time Axis Partition of the Piecewise Exponential Model

The partition of the time axis is motivated by the nature of the endpoint; by definition, most of the component events that make up the composite safety event (CSE) occur within 7 days. Late onset components can happen between 7 days and 360 days, but these are expected to be rare.

Censoring Procedures

The model in part B, above, is based on censoring or event times up through Follow-up Day 360. Subjects without a known event will be considered censored at the last scheduled or unscheduled case report form (CRF) date. When fitting the piecewise exponential models, all events and censoring times > 360 days will be assigned a time of 360 Days.

Predictive Probabilities and Posterior Inference

At every analysis, the imputations described above are executed $M=5000$ times, resulting in M completed datasets, filled with only E or N final outcome values. With the $\text{Beta}(0.5, 0.5)$ prior distributions specified in Section 10.1, each of the M completed datasets implies a conjugate Beta posterior distribution for both Q_T and Q_C . From these, the posterior probability $\text{Pr}(Q_T < Q_C + 0.08 | m^{\text{th}}$ completed dataset) is computed. This is used in the following ways:

- At each sample size look: The proportion of these M completed datasets that results in $\text{Pr}(Q_T < Q_C + 0.08 | m^{\text{th}}$ completed dataset) $> \Psi_{\text{saf}}$ is the predictive probability of future success for the safety objective. As described in Section 12, this is used to determine whether to curtail enrollment.
- At the final analysis: For the final analysis, an identical model serves as the “imputer’s model” in a Bayesian multiple imputation that is used to account for any missing data in the inferential tests of the primary endpoint. Averaging the values $\text{Pr}(Q_T < Q_C + 0.08 | m^{\text{th}}$ completed dataset) over the set of M completed datasets integrates over the posterior predictive distribution of imputed values and results in a final (combined) posterior probability $\text{Pr}(Q_T < Q_C + 0.08 | \text{data})$ that is compared to the threshold Ψ_{saf} to determine whether non-inferiority has been statistically established. This is Bayesian multiple imputation.

14 Operating Characteristics of the Design

The design described above has been subjected to extensive simulation in order to evaluate its anticipated performance in a variety of scenarios. In the simulation, power is determined as the proportion of simulated trials that result in a simultaneous declaration of non-inferiority for both effectiveness and safety at the final analysis. All results are based on 10,000 simulated trials (per scenario studied), with predictive probabilities and multiple imputation implemented using $M=5000$ observations from the relevant posterior predictive probability distributions.

Table 2 displays the power and sample size behavior of the design in the specific case that $P_T = P_C = 0.65$ and $Q_T = Q_C = 0.08$. Of the 10,000 trials in this simulation, 1900 simulated trials stopped enrolling at the

N=350 analysis because the interim results were promising (i.e., the predictive probabilities of future success for both effectiveness and safety exceeded their respective thresholds); 40 trials stopped enrolling at the N=350 analysis for futility (i.e., at least one of the predictive probabilities of future success, for efficacy or for safety, was less than its respective threshold). Of the 8060 trials that did not stop at the N=350 analysis, 3523 stopped enrolling for promising trend at the N=450 analysis, while 69 stopped enrolling for futility. The table shows other possibilities, including the fact that 813 of the 10,000 trials enrolled the full maximum of N=750. The final column (“SSavg”) indicates the expected sample size to be 504 subjects, calculated as the weighted average of the various sample sizes, weighted by their frequency of occurrence. Of all 10,000 trials, 9635 ended in a simultaneous determination of non-inferiority for both effectiveness and safety, so the estimated power for this scenario is 0.9635.

Table 2 Operating Characteristics for Target Scenario, assuming PC = 0.650, QC = 0.08.

P _T	Q _T	Power	Probability of Stopping Enrollment at ...					SSavg
			N=350	N=450	N=550	N=650	N=750	
0.650	0.080	0.9635	0.1900 0.0040	0.3523 0.0069	0.2402 0.0032	0.1189 0.0032	0.0813	504

In the columns labeled N=350, N=450, N=550, and N=650, the upper entry for each scenario is the estimated probability that the trial will stop enrolling at that size for promising trends; the lower entry for each scenario is the estimated probability that the trial will stop enrolling at that size for futility. All estimates are based on 10,000 simulated trials.

Table 3 displays similar operating characteristics as the values P_T and Q_T assume different values—some more optimistic than those in **Table 2**, and some less so. Power is seen to range from 0.7891 in the first row (most pessimistic scenario), with the largest average sample size, to 0.9926 in the last row (most optimistic), with the smallest average sample size. Overall, the design displays good power for scenarios of interest, and the sample size determination algorithm responds appropriately as it learns the strength of the accruing evidence.

Table 3 Operating Characteristics for Various Scenarios, assuming PC = 0.650, QC = 0.08.

Scenario		Power	Probability of Stopping Enrollment at					SSavg
P _T	Q _T		N=350	N=450	N=550	N=650	N=750	

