 For re-ablations occurring Day 1-75, pre-procedural imaging is not required. For re-ablations scheduled for Day 76 or later, ensure the Day 90 cardiac MRI/CT is performed before re-ablation.

 Month 12 cardiac MRI/CT only if 3-month imaging revealed any PV with ≥ 70% reduction in PV measured diameter.

 Performed at the beginning of the procedure prior to ablation. See **Section 5.3** for managing subjects whose procedure is delayed by intracardiac thrombus.

 Only if resolution of phrenic nerve palsy has not yet been demonstrated. May be performed either by fluoroscopic sniff test or inspiration/expiration CXR.

 Non-NAS subjects: If NIHSS score has increased by 1 or more points or if there is a clinical suspicion of stroke/TIA, then a consulting neurologist will perform a stroke assessment and include the results of a concurrent brain MRI. If stroke is diagnosed, a Modified Rankin Scale assessment will be performed prior to discharge and again at 3 months.

 NAS subjects: If NIHSS score has increased by 1 or more points, if there is a clinical suspicion of stroke/TIA, or if the post-procedural brain MRI is positive for SCE or SCL findings then a consulting neurologist will perform a stroke assessment and include review of the NAS post-procedural brain MRI. If stroke is diagnosed, a Modified Rankin Scale assessment will be performed prior to discharge and again at 3 months.

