11.1 Safety Estimation

Although the pre-specified statistical analysis methods are Bayesian, standard frequentist considerations are used to guide sample size selection. The sample size for primary safety computed for a Farrington-Manning test with PASS 13¹¹ indicates that, for 1:1 randomization, 90% power, alpha=0.05 (one-sided), CSE rate in both Groups of 0.08 and non-inferiority margin of 0.08, the study requires a completed sample size of 214 subjects in each Group, for a total of 428. Assuming a 5% rate of loss-to-follow-up (LTFU), 450 subjects are needed.

There is uncertainty in the CSE rate, and this can have dramatic impact on sample size requirements. If the CSE rate is 0.07 in the Pulsed Field group but 0.08 in the Thermal group, 326 subjects are required to achieve 90% power (344 after compensating for 5% LTFU). If the CSE rate is 0.10 in the Pulsed Field group but 0.08 in the Thermal group, 690 subjects are required to achieve 85% power (727 after compensating for 5% LTFU). Interim analyses can also increase the sample size requirement. This uncertainty in the CSE rate motivates the use of a design wherein the sample size is adaptively determined, with possible sample sizes ranging from 350 to 750.

Overall statistical power for the study depends on power for the primary effectiveness test as well as the primary safety test. Power is more thoroughly estimated by simulation and is described in Section 14.

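### A Month 12 completer who never had an evaluable post-ablation scan is entered as a known non-event for pulmonary vein stenosis in the primary safety analysis

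*SAP*

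**What the plan says.** - **Component.** Stenosis is one of two late-onset CSE components (Protocol 7.1). Table 5 defines it by core-lab measurement of vein diameter on CT/MRI against the baseline scan.
- **Measurement.** Protocol 4.7.7 schedules one post-ablation scan for every ITT subject, at Day 90 ± 14. Footnote 6 of Table 3 makes the later scan conditional: "Month 12 cardiac MRI/CT only if 3-month imaging revealed any PV with" a reduction of at least 70%. A missed Day 90 scan therefore has no scheduled replacement.
- **Status rule.** SAP 13.2, category A (final status known): "This can also happen if the subject is event-free as of the 12-month assessment". Category B, the only group that is imputed: "Subject is censored without known event prior to the 12-month assessment".
- **Censoring rule.** SAP 13.2: "Subjects without a known event will be considered censored at the last scheduled or unscheduled case report form (CRF) date". Also, "all events and censoring times > 360 days will be assigned a time of 360 Days".
- **Completion.** SAP 4.1.10 defines a Completed Subject by the Month 12 Assessment, in person or remote, with no imaging condition.
- **Sensitivity analyses.** SAP 16.1.1 limits the completers-only and tipping-point analyses to subjects lost to follow-up or with a permanently missing effectiveness outcome.

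**The concern.** A component that can be established only by imaging is scored as absent when no imaging was done. The SAP does not treat its other endpoints this way. In 13.1, effectiveness follow-up ends at the last event monitor or Holter, that is, at the last actual measurement. In 10.2.1, the vein-area endpoint is restricted to subjects with both pre- and post-procedure vein data. The same unscanned subject is thus unavailable for the secondary safety endpoint but a known non-event for the primary one.

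There are two consequences. The arm's CSE rate is understated by whatever stenosis went undetected. The unscanned days also enter T_2, the exposure for the hazard λ2 between Days 7 and 360, as event-free time, which lowers the imputed risk for other subjects in that arm. The simulations (SAP 15.5) model missing safety data only as 5% loss to follow-up, so they do not test this.

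**Working it through.** **1. The plan's own sample size.** Inputs from SAP 11.1: "for 1:1 randomization, 90% power, alpha=0.05 (one-sided), CSE rate in both Groups of 0.08 and non-inferiority margin of 0.08". The Farrington-Manning restricted rates under the null are 0.1353 and 0.0553.

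- s0 = √(0.1353×0.8647 + 0.0553×0.9447) = 0.4114
- s1 = √(2×0.08×0.92) = 0.3837
- n per group = [(1.6449×0.4114 + 1.2816×0.3837)/0.08]² = 213.3, rounded up to 214

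This matches the SAP: "the study requires a completed sample size of 214 subjects in each Group, for a total of 428". For dropout, 428/0.95 = 450.5, against the stated 450.

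**2. The SAP's late-onset rates (SAP 15.3).**

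- Default (Saf1): S(7) = exp(−7×0.011137363) = 0.925; S(360) = exp(−7×0.011137363 − 353×0.000015354) = 0.920. Late onset: 0.5 points.
- Stress (the three-interval alternative): S(7) = 0.95, S(180) = 0.93, S(360) = 0.92. Late onset: 3 points.

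Both cover all late-onset events, including fistula, so as stenosis rates within each scenario they are upper limits.

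**3. What the rules do to an unscanned subject with no other CSE.** SAP 13.2 imputes an event with probability θ = (S(R) − S(360))/S(R), where R is the censoring day.

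- Reaches Month 12: category A, status N. Through the formula, R = 360 also gives θ = 0. The subject is N in every completed dataset.
- Leaves early: credited as event-free to R, then imputed for the remaining days only.

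| Last CRF (day) | θ, default | θ, stress |
|---|---|---|
| 60 | 0.46% | 2.5% |
| 104 | 0.39% | 2.0% |
| 180 | 0.28% | 1.1% |
| 330 | 0.05% | 0.2% |
| 360 or later | 0 | 0 |

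**4. Size of the understatement.** Let m be the share of an arm that reaches Month 12 unscanned and p the stenosis risk. The documents give no value for m, so a range is assumed. The arm's CSE rate is understated by m×p.

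| m (assumed) | p = 0.5% | p = 3% |
|---|---|---|
| 5% | 0.025 points | 0.15 points |
| 10% | 0.05 points | 0.30 points |
| 20% | 0.10 points | 0.60 points |

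Against the 8-point margin, the 10% row is 0.05/8 = 0.6% and 0.30/8 = 3.75%.

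**5. Effect on the test.** Exact enumeration of the Beta(0.5, 0.5) test at the 0.966 threshold, with a fixed 225 per arm:

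| Case | Power at 0.08/0.08, misses in Thermal only | False acceptance at 0.16/0.08, misses in Pulsed Field only |
|---|---|---|
| No missed stenosis | 0.8995 | 0.0356 |
| m 10%, p 0.5% | 0.8967 | 0.0369 |
| m 10%, p 3% | 0.8822 | 0.0441 |
| m 20%, p 3% | 0.8626 | 0.0541 |

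These are fixed-size illustrations. They do not reproduce the adaptive simulation in SAP Table 4, which reports 0.0528 for safety.

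**The case against.** The strongest reply has four parts.

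- **Direction.** If stenosis is mainly a thermal injury, missed cases lower the control rate and make non-inferiority harder to show. This stands. A reader might infer that the rule tilts the comparison toward the device; the documents do not support that as a general statement. Only stenosis missed in the Pulsed Field arm does so.
- **Size.** A reader might take the two severe RF veins of 166 in Protocol Table 1 (1.2%), multiply by two to four veins per subject to get 2.4–4.8%, assume 10–15% missing scans, and arrive at 0.24–0.72 points. The documents do not support this. Table 1 gives no subject counts, the missing-scan share has no source, and RF may be only 40–60% of Thermal Subjects under Protocol 9.2. The stenosis rates also far exceed the SAP's default late-onset total of 0.5 points. In addition, a CSE must be a related SAE adjudicated by the CEC, so an imaging rate is not automatically a CSE rate.
- **Safeguards.** Protocol 4.7.7 allows an off-site or delayed scan under COVID-19 disruption, 4.7.12 gives cardiac imaging priority, and a scan is required before vein re-ablation from Day 76. Clinically prompted imaging may also find stenosis. These reduce m but do not change the status of a subject who remains unscanned. Protocol 9.1 says data on COVID-related missed assessments will be used as required for sensitivity analyses, but it sets no rule for this case.
- **Scope.** A reader might infer that every unscanned subject is counted as stenosis-free. That is too broad, because those who exit before Month 12 fall in category B and are imputed.

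None of this answers the category A problem for unscanned completers.

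**Conclusion.** The point holds for one group: subjects who reach Month 12 with no evaluable post-ablation scan and no other CSE. They are entered as known non-events on a component that was not measured, and no planned sensitivity analysis in SAP 16.1.1 covers them. This follows from reading category A together with the last-CRF rule; the SAP has no missing-scan rule of its own.

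The effect is probably small: about 0.05 to 0.30 points on the affected arm's CSE rate. That range rests on an assumed 10% unscanned and on treating the SAP's late-onset totals as the stenosis risk. It becomes material only if many scans are missed and stenosis is more frequent than the SAP's default expects. The direction depends on the arm in which stenosis is missed. The case for changing the rule is that it assigns an unsupported status within a co-primary endpoint and is cheap to correct.

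**What to change.** In SAP 13.2:

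- Allow category A status N only if an evaluable post-ablation vein scan exists.
- Place a subject with no CSE whose scan window has passed without an evaluable scan in category B. Use Day 104, or the end of a documented COVID-19 delay. Censor at Day 7, the end of the early-onset window, or at the last CRF if earlier.
- Leave subjects whose scan is not yet due as they are now. This matters at the interim looks.

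The existing λ2 model then imputes late-onset risk once. From Day 7, θ is 1 − 0.920/0.925 = 0.54% (default) or 1 − 0.92/0.95 = 3.2% (stress). A separate stenosis imputation should not be added: λ2 already carries that risk, so it would be counted twice for early exits and for interim subjects awaiting their scan.

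In SAP 16.1.1, add these subjects to the tipping-point analysis, and report missing scans by arm.

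**Cost.** A few lines of text and code. The safety missing fraction rises somewhat above the 5% simulated. As an upper bound, treating the unscanned as fully missing gives 428/0.90 = 476 (5% loss plus 5% unscanned) or 428/0.85 = 504 (5% plus 10%), both within 350–750. Censoring at Day 7 also discards these subjects' clinical follow-up for fistula, a small loss for an event expected to be rare.
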